#### Endpoints related to objective #7: Change in functional status

The endpoints for this objective will assess changes in functional status (i.e., work/school/pre-school attendance, mobility, and performance status) between the index date and key time-points following the index date (Table 6-1). The number (%) of patients attending work/school/pre-school will be summarized at the index date and at each time-point. In addition, the number (%) of patients with work/school/pre-school attendance (e.g., full-time; part-time, no attendance; part-time) will be presented at each time-point along with the reason for change status. Frequency counts and percentages will also be presented for the number (%) of patients with mobility between the index date and key time-points following the index date (Table 6-1). Performance status scores (i.e., ECOG, Lansky, Karnofsky) will be described and presented at the index date and at key time-points following the index date along with the number (%) of

patients with a change between the index date and key time-points following the index date (Table 6-1).

Endpoints related to objective #8: Change in HRU

The endpoints for this objective will assess changes in HRU (e.g., ER visits, hospitalizations) over time during the study period and key time-points following the index date (Table 6-1). The mean (SD) rate of hospitalizations and ER visits will be presented during the pre-index period and between the index date and over time during the study period. Frequency counts and percentages will also be presented for the number (%) of patients experiencing at least one hospitalization and at least one ER visit, separately, during the pre-index date period and study period. The mean (SD) number of ER visits and the mean (SD) duration of hospitalization will also be presented during the pre-index date period and over time during the study period.

Endpoints related to objective #9: Change in clinical assessments such as laboratory evaluation, vital signs and physical findings over time

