1.2 Study objectives

Primary objective

To describe the efficacy of alpelisib as measured by the proportion of patients with response (yes/no) at Week 24 or 6 months (+/- 4 weeks), defined by achieving at least 20% reduction from index date in the sum of measurable target lesion volume (1 to 3 lesions, via central review of imaging scans), provided that none of the individual target lesions have $\geq 20\%$ increase from index date and in absence of progression of non-target lesions and without new lesions.

Secondary objectives

1. To assess changes in the sum of measurable target lesion (1 to 3 lesions) volume over time
2. To assess changes in the sum of all measurable (target and non-target) lesion volume over time
3. To assess changes in the sum of all measurable non-target lesion volume over time
4. To assess the duration of response defined as the time from first documented response, to the date of the first documented disease progression or death due to any cause.
5. To assess type of medication and non-drug therapies (e.g., concomitant PROS-related medications, PROS-related surgeries, duration of treatment/response) over time
6. To assess changes in PROS symptoms and complications (e.g., chronic bleeding/leaking, pain) over time
7. To assess changes in functional status (e.g., work/school/pre-school attendance, mobility) over time
8. To assess changes in HRU (e.g., ER visits, hospitalizations) over time
9. To assess changes in clinical assessments such as laboratory evaluation, vital signs and physical findings over time
10. To assess the safety and tolerability of alpelisib

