- Truly non-measurable lesions (for example, superficial visual lesions, masses, organomegaly, PROS-related enlargement of anatomic area identified by physical exam that is not measurable by reproducible imaging technique)
- Definition of new lesion will be detailed in the in the Independent Central Review Charter.

2 Changes to the protocol specified analysis

The following update on time windows were implemented following outcome of internal audit conducted in early Jan 2021.

The time window was extended for the baseline imaging scans to include imaging scans performed up to 24 weeks prior to index date, instead of 12 weeks as indicated in the protocol, to allow for flexibility given the retrospective/real world nature of the EPIK-P1 study. The extension to the time window is intended to reflect the majority of the local medical practice and to include the maximum number of patients for the primary analysis. Furthermore, the extension to the time window is unlikely to modify the baseline assessment significantly as there is not published evidence that the disease may spontaneously improve.

The time window was extended for the 24 weeks scan to include imaging scan assessments between 20 weeks and 31 weeks for the primary endpoint as well as other endpoints, instead of 20 to 28 weeks as reported in the protocol. In accordance with clinical practice in the real world setting, some physicians conducted the imaging scan assessments at 6 months (corresponding to ~ 27 weeks). As such the time window was extended (24 weeks or 6 months +/-4 weeks) to estimate the 24 week endpoints efficiently.

3 Data analysis information

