For alpelisib a dose reduction is defined as a decrease in dose from the starting dose (e.g. from 250 mg daily to 200 mg daily) even if the dose decrease has been directly preceded by an interruption. On the other hand, if the dose decrease is followed by an interruption, with the dose resuming at the same level prior to the interruption (e.g. in the sequence 250 mg daily – 0 mg - 250 mg daily), the second dose decrease or change in dosing frequency will not be counted as dose reduction.

An interruption is defined as a zero dose on one or more days between two non-zero doses.

A dose increase is defined as an increase as compared to the starting dose level. Note that a dose rechallenge i.e when a patient goes back to the previous prescribed dose after an interruption, is not considered as an increase.

Table 3-4 Endpoints related to objective #5

Measure	Type of variable	Summary Statistics	Timing
Duration of exposure to alpelisib	Continuous	N, mean, median, standard deviation, Q1, Q3, minimum and maximum	Overall during study period
Alpelisib average daily dose; cumulative dose; dose intensity; relative dose intensity	Continuous	N, mean, median, standard deviation, Q1, Q3, minimum and maximum	Overall during study period
Proportion of patients that discontinued alpelisib	Binary	Frequency, percentage	Overall during study period;
Reason for discontinuation of alpelisib	Categorical	Frequency, percentage	Overall during study period;
Proportion of patients with an alpelisib dose adjustment	Binary	Frequency, percentage	Overall during study period
Proportion of patients with an alpelisib dose interruption	Binary	Frequency, percentage	Overall during study period
Reason for alpelisib dose interruption	Categorical	Frequency, percentage	Overall during study period

Measure	Type of variable	Summary Statistics	Timing
Number of alpelisib dose interruptions and/ or discontinuations	Continuous	N, mean, median, standard deviation, Q1, Q3, minimum and maximum	Overall during study period
Proportion of patients receiving PROS-related medication	Binary	Frequency, percentage	Overall during study period; At key time points
Indication of treatment for PROS-related medication	Categorical	Frequency, percentage	Overall during study period; At key time points
Proportion of patients receiving non-drug treatment by type (e.g., feeding tube, ketogenic diet)	Categorical	Frequency, percentage	Overall during study period;

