For the ECOG scale, "improvement" is defined as a decrease by at least 1 point and "worsening" is defined as an increase by at least 1 point. For the Karnofsky and Lansky scale, "improvement" is defined as an increase by at least 20 points and worsening is defined as a decrease by at least 20 points. For example if a patient reports a score of 100 ("Normal, no complaints") at index date and a score of 80 ("Care for self. Unable to carry on normal activity or to do active work") would be considered as "worsening" while a score of 90 will still be considered as "stable". This approach takes into account the criteria for correspondence between the ECOG and Karnofsky/Lansky scale to make the categorization comparable and consistent between the scales. Results from other scales will be listed, if reported.

Importantly, based on feasibility discussions with study sites, it is anticipated that there will be variability in the use of the listed performance status measurement tools, based on preference of each institution, as well as variability on whether a performance measure is utilized for each patient (given the heterogeneity in the complications experienced by PROS patients).

Table 3-6 Endpoints related to objective #7

Measure	Type of variable	Summary Statistics	Timing
Proportion of patients that attend work/school/pre-school, overall and by type (i.e., full-time, part-time, no attendance)	Categorical	Frequency, percentage	At index date
Proportion of patients with "improvement", "worsening" and "stable" in work/school/pre-school attendance	Categorical	Frequency, percentage	At key time-points
Proportion of patients with any mobility assessments	Binary	Frequency, percentage	At key time-points
Severity of mobility impairment (i.e., no, mild, moderate, severe, total impairment)	Categorical	Frequency, percentage	At key time-points
Proportion of patients with a functional assessment (i.e., ECOG, Karnofsky, Lansky, other) performed	Binary	Frequency, percentage	At index date
Functional assessment score (ECOG, Karnofsky, Lansky)	Continuous	N, mean, median, standard deviation, Q1, Q3, minimum and maximum	At index date
Proportion of patients with "improvement", "worsening" and "stable" in functional assessment (ECOG, Karnofsky, Lansky)	Binary	Frequency, percentage	At key time-points

Endpoints related to secondary objective #8: Change in Healthcare resource use (HRU)

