An important aspect of treatment with alpelisib consist in the healthcare resources needed to care for patients with PROS. The necessity for frequent hospitalization and ER visits could have both an economic and a general health impact on PROS patients. The analyses below aims to describe the pattern observed in the study population.

The proportion of patients using non-medical resource, hospitals and ER visits will be reported, along with the relation to the disease, during the study period.

Moreover the same measure will be assessed as available for the pre-index period and reported separately, to assess the use of HRU and ER visits prior to start of alpelisib.

Table 3-7 Endpoints related to objective #8.

Measure	Type of variable	Summary Statistics	Timing
Proportion of patients using non-medical resource (e.g., physical therapy, occupational therapy, home school)	Binary	Frequency, percentage	Overall during study period
Proportion of patients using non-medical resource due to PROS (i.e., related or not related)	Binary	Frequency, percentage	Overall during study period
Frequency of non-medical resource use	Categorical	Frequency, percentage	Overall during study period
Proportion of patients with ≥ 1 hospitalization	Binary	Frequency, percentage	Overall during study period
Proportion of patients with ≥ 1 hospitalization related to PROS (i.e., related or not related)	Binary	Frequency, percentage	Overall during study period
Number of hospitalizations	Continuous	N, mean, median, standard deviation, Q1, Q3, minimum and maximum	Overall during study period
Number of hospitalizations related to PROS	Continuous	N, mean, median, standard deviation, Q1, Q3, minimum and maximum	Overall during study period
Duration of hospitalizations	Continuous	N, mean, median, standard deviation, Q1, Q3, minimum and maximum	Overall during study period
Duration of hospitalizations related to PROS	Continuous	N, mean, median, standard deviation, Q1, Q3, minimum and maximum	Overall during study period
Proportion of patients with ≥ 1 ER visit	Binary	Frequency, percentage	Overall during study period
Proportion of patients with ≥ 1 ER visit related to PROS (i.e., related or not related)	Binary	Frequency, percentage	Overall during study period
Number of ER visits	Continuous	N, mean, median, standard deviation, Q1, Q3, minimum and maximum	Overall during study period

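### SAP Table 3-7 drops, undeclared, the protocol's hospitalization and ER-visit rates and their reporting over time, so change in healthcare resource use cannot be quantified

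*SAP*

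**What the plan says.** **Protocol 6.8.2, objective #8**, plans three kinds of summary:

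- A rate: "The mean (SD) rate of hospitalizations and ER visits will be presented during the pre-index period and between the index date and over time" in the study period.
- The mean number of ER visits and mean duration of hospitalization, which "will also be presented during the pre-index date period and over time during the study period".
- The number and percentage of "patients experiencing at least one hospitalization and at least one ER visit, separately, during the pre-index date period and study period".

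The same section ties the assessment of change to the key time-points of Protocol Table 6-1.

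**SAP 1.2** keeps the objective: "To assess changes in HRU (e.g., ER visits, hospitalizations) over time". **SAP 3.6, Table 3-7** (numbered 3-6 in the SAP's list of tables) has 13 rows: proportions, one frequency category, numbers and durations. None is a rate, and every row is timed over the study period as a whole. For the time before treatment, the SAP adds: "Moreover the same measure will be assessed as available for the pre-index period and reported separately". That sentence follows one about proportions of users, so it is not clear that it also covers counts and durations. SAP 3.4 plans a pre-index frequency of hospitalizations and ER visits, without a time unit.

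**SAP Section 2**, which lists changes to the protocol-specified analysis, opens: "The following update on time windows were implemented following outcome of internal audit conducted in early Jan 2021". It goes on to describe the baseline and Week 24 imaging windows and does not mention HRU.

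**The concern.** Counts of events, and the share of patients with at least one event, grow with the time observed. Here that time differs between the two periods and between patients. A rate is the natural summary that allows for this, and the protocol named one. Reporting by time window would also have shown the course after the index date. Without either, a reader who sets the study-period figures beside the pre-index figures cannot tell how much of a difference comes from HRU and how much from length of observation.

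At stake is the reading of one descriptive secondary objective. The primary endpoint is unaffected. It still deserves correction, because Protocol 9 intends the results for submission to health authorities and because Section 2 is where a reader would look for a dropped summary.

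The point covers hospitalizations and ER visits only. The percentages with at least one event are in the protocol too and are not an SAP error.

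**Working it through.** **Inputs**

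- Pre-index period: at most 24 weeks (SAP 1.3). Full coverage is not assured, because inclusion criterion 6 (Protocol 6.2.1) requires chart history only during enrollment in the managed access program.
- Study period: index date to 09-Mar-2020, with data after discontinuation limited to 30 days past the last dose (SAP 1.3).
- Latest permitted index date: 23-Sep-2019 (Protocol 6.2.1, criterion 5).
- Follow-up beyond 24 weeks is expected for many patients (SAP 3.6), and windows at 63 and 74 weeks are planned (SAP 3.3).

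**The plan's own figure.** From 23-Sep-2019 to 09-Mar-2020 is 168 days, and 168/7 = 24.0 weeks. The stated minimum reproduces. No upper limit on follow-up is stated.

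**Who has less than 24 study weeks.** With the 30-day tail, observed time reaches 24 weeks for anyone stopping at week 24 − 30/7 = 19.7 or later, barring death. Only earlier stoppers fall short.

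**Count ratio under an unchanged rate.** Expected count = rate × weeks observed, so the ratio of study to pre-index count is T_study / T_pre. The change in rate that would leave the counts equal is T_pre / T_study − 1. The follow-up times below are illustrative.

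| Patient | T_study (weeks) | Ratio, T_pre = 24 | Rate change hidden by equal counts | Ratio, T_pre = 12 (assumed) |
|---|---|---|---|---|
| Stops at week 8 | 8 + 30/7 = 12.29 | 12.29/24 = 0.51 | 24/12.29 − 1 = +95% | 12.29/12 = 1.02 |
| 24 weeks | 24 | 24/24 = 1.00 | 0% | 24/12 = 2.00 |
| 52 weeks | 52 | 52/24 = 2.17 | 24/52 − 1 = −54% | 52/12 = 4.33 |

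On a rate scale with the correct denominators, every ratio would be 1.00.

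**Share with at least one event.** This also rises with time, by an amount that depends on the event rate and on how it varies between patients. The documents give neither. Assume one constant Poisson rate for all patients, so that the share is 1 − exp(−rate × T). From 24 to 52 weeks with no true change, it goes from 18% to 35% at 0.2 events per 24 weeks, from 39% to 66% at 0.5, and from 63% to 89% at 1.0. At 0.5, a true halving of the rate would still show 42% at 52 weeks against 39% before.

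**What a fall in counts can show.** Let N be the number of events. If T_study ≥ 24 ≥ T_pre and N_study < N_pre, then N_study/T_study ≤ N_study/24 < N_pre/24 ≤ N_pre/T_pre. For such patients a fall in counts does mean a fall in rate. An unchanged count does not say how far, if at all, the rate fell, and a rise cannot be interpreted.

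**The case against.** **The retained figures are informative.** A reader might infer that Table 3-7 cannot show change at all. The documents do not support that. Patients on treatment at cut-off, and most who stop at about week 20 or later, have at least as much study time as pre-index time. As shown above, a fall in their counts is evidence of a fall in rate. Incomplete pre-index records, and the SAP 4.3.1.1 rule that places undated events in the study period, make such a fall harder to see, not easier. This stands, with one limit: Table 3-7 does not split patients by follow-up, so early stoppers are mixed into the totals.

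**More than counts and percentages remains.** Duration of hospitalization is kept, all-cause and PROS-related. If it means length per stay, it depends much less on follow-up. The SAP does not say whether it is per stay or total days.

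**Study-period time can be approximated.** SAP 3.6 summarizes duration of exposure, including interruptions, up to the cut-off date for patients still on treatment. That is close to study-period person-time, less the 30-day tail for those who stopped. It supplies only the study half; no pre-index denominator is planned.

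**The protocol's rate has no stated denominator.** The SAP's number of hospitalizations may be how that rate was carried over. This is possible for hospitalizations but weaker for ER visits, where the protocol lists a rate and a number separately.

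**Whole-period timing is common in the SAP.** In the objective #5 table only 2 of 16 rows are timed "Overall during study period; At key time points", and the surgery rows are whole-period. That shows the SAP names key time-points where it wants them. It does not make HRU an exception among event summaries.

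**The analysis is descriptive.** No test or formal before/after contrast is prescribed. The point asks for none, only for the descriptive summary that the protocol named.

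**An earlier log entry may exist.** The SAP version history is partly redacted, so this cannot be excluded. Section 2 is readable and silent.

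**Conclusion.** The point holds in this form. The protocol's hospitalization and ER-visit rates and its over-time HRU reporting are absent from SAP Table 3-7, and Section 2 does not declare it. Change in HRU cannot be quantified from what remains without a time denominator.

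The size is known only by illustration: under an unchanged rate, the expected count ratio runs from 0.51 (stopping at week 8) to 2.17 (52 weeks). This assumes a constant rate, a full 24-week pre-index record and equally complete recording in both periods. The documents give no follow-up distribution and no HRU rate, so no cohort figure follows, and the net direction of the distortion is not known. Longer follow-up pushes apparent HRU up, and early discontinuation pushes it down. A reader might infer that the figures are bound to favour alpelisib, or to count against it; neither can be shown.

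**What to change.** 1. In Table 3-7, restore hospitalization and ER-visit rates for both periods as events per person-time, showing total events and total person-time. State whether the mean (SD) is of per-patient rates.
2. Run study-period time from the index date to the end date already defined under SAP Table 4-2. Add a rule for observed pre-index time, for example a full 24 weeks versus time since the first chart record, shown as a range.
3. Restore the protocol's over-time reporting by the SAP Table 3-1 windows. Use time under observation in each window as denominator, not the SAP 3.3 count of patients with an assessment.
4. Keep whole-period counts and percentages, labelled with length of observation and not described as change. State whether hospitalization duration is per stay or total.
5. Record any remaining departure from Protocol 6.8.2, with its reason, in SAP Section 2.

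PROS-related rates, time to first event, and rates with and without undated events would go beyond the protocol and are optional.

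**Cost.** SAP wording and some table programming. Pre-index person-time may rest on an assumption, because those data are taken only as available, and per-patient rates from short follow-up are unstable. A rate corrects for observation time only. It does not remove regression to the mean in patients whose condition was judged severe or life-threatening when treatment began.

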The endpoints for this objective will assess changes in patient's clinical assessments (e.g., laboratory assessments, vital signs) between the index date and key time-points following the index date (Table 6-1). The change in clinical assessments will be summarized as the number (%) of patients experiencing a change in each clinical assessment. Changes in clinical assessments from the index date will also be presented as shift tables. Growth and development information will also be summarized for patients who were aged <18 years at the time of first dose and until the age of 18 years.

Endpoints related to objective #10: Type, frequency, seriousness, and severity per CTCAE v4.03 criteria and causality assessments of treatment-emergent adverse events

The endpoint will report adverse events defined as the appearance of (or worsening of any pre-existing) undesirable sign(s), symptom(s), or medical condition(s) that occur during the study period. As much as possible, each adverse event will be evaluated to determine:

1. Toxicity grade
2. Duration
3. Relationship to the study treatment (i.e., not related, related, unknown)
4. Whether it is serious as per medical chart (seriousness and seriousness criteria established during the MAP)
5. Action taken with respect to study treatment (i.e. dose increased; dose not changed; dose reduced; drug interrupted; drug withdrawn)
6. If a concomitant medication or additional therapy was provided (for example diet for impaired glycemic control)
7. Outcome (i.e., not recovered/not resolved, recovered/resolved, recovering/resolving, recovered/resolved with sequelae, fatal, unknown)

Adverse events will be summarized as: the number (%) of patients experiencing each adverse event, (the number (%)) of patients experiencing any CTCAE grade 3 or higher adverse event, the number (%) of patients with serious adverse events, the number (%) of events related to treatment, the number (%) of patients who received a concomitant or an additional treatment

due to adverse event. For adverse events requiring dose interruption, the duration of interruption will be reported.

Adverse events will be coded using the Medical dictionary for regulatory activities (MedDRA) terminology. The latest available MedDRA version at the time of the analyses will be used.

The outcome of adverse events will be presented as the number (%) of patients with each outcome after any event (e.g., number [%] of patients that did not recover from any event).

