1.3 Study design and settings

This study will be a site-based retrospective non-interventional medical chart review of pediatric and adult male and female patients with PROS.

Patients with PROS who have received at least one dose of alpelisib initiated at least 24 weeks before the cutoff date (09-Mar-2020) through a Novartis Managed access program (MAP) and satisfy the study inclusion criteria will be included in the study.

Patient-level data will be abstracted from medical charts of all eligible patients at all participating sites and will be pooled and assessed. Trained personnel at each site will abstract medical chart data. Informed consent will be obtained prior to data abstraction, as appropriate, for eligible patients interested in participating in the study where required.

[figure not shown]
The cut-off date of 09-Mar-2020 is selected to minimize the impact of the COVID-19 pandemic on the data integrity. Eligible patients who were initiated alpelisib on or before 23-Sep-2019 are expected to have 24 weeks of relevant assessments on or before 09-Mar-2020. At that time of the cut-off, COVID-19 pandemic did not have major consequences on the regular management of the patients in the countries participating in the MAP.

The **study period** will be defined as the period from the index date up to the cut-off date (09-Mar-2020) (Figure 1-1). During the study period all available data will be collected, if a patient has discontinued treatment prior to the cut-off date only data reported up to 30 days after the last date of study treatment will be abstracted and entered into the database.

The **index date (baseline)** will be defined as the date of alpelisib initiation. This date will be used as reference date for all assessments (safety and efficacy).

The **pre-index date** period will be defined as the period from up to 24 weeks prior to the index date (baseline) through to the day prior to the index date. (Figure 1-1).

Figure 1-1 Study design

Lesion assessments and definition

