Number of ER visits related to PROS	Continuous	N, mean, median, standard deviation, Q1, Q3, minimum and maximum	Overall during study period

Endpoints related to secondary objective #9: Change in clinical assessments such as laboratory evaluation, vital signs and physical findings over time

The following endpoints will assess changes in patient’s clinical assessments cardiac (e.g., ECG, BNP) and laboratory assessments (e.g., D-dimer, fibrinogen, hemoglobin) as well as vital signs (e.g., height, weight, blood pressure, pulse oximetry) between the index date and key time-points following the index date, appropriately by age groups.

The following summaries will be produced for laboratory data (by laboratory parameter):

- Worst post-baseline Common Toxicity Criteria (CTC) grade. Each patient will be counted only for the worst grade observed during study period.
- Shift tables using CTC grades to compare index date to the worst collected value during study period.
- For laboratory tests where CTC grades are not defined, shift tables using the low/normal/high/(low and high) classification to compare index date to the worst collected value during study period.

Vital signs assessments are reported in order to characterize basic body function. The parameters expected to be collected may include: height, weight, respiratory rate, systolic and diastolic blood pressure. The number and percentage of patients with notable vital sign values (high/low) will be presented. A listing of all vital sign assessments will be produced and notable values will be flagged.

Clinically notable vital sign criteria are provided [Table 3-8](#) below.

Table 3-8 Clinically notable changes in vital signs

Vital sign		Patient age at visit	
		< 18 years	≥ 18 years
Systolic blood pressure [mmHg]	High	≥ 95th percentile of the age and height group ¹	≥ 180 with increase from updated baseline ⁵ of ≥20 mmHg
	Low	≤ 5th percentile of the age and height group ¹	≤ 90 with decrease from updated baseline ⁵ of ≥20 mmHg
Diastolic blood pressure [mmHg]	High	≥ 95th percentile of the age and height group ¹	≥ 105 with increase from updated baseline ⁵ of ≥15 mmHg
	Low	≤ 5th percentile of the age and height group ¹	≤ 50 with decrease from updated baseline ⁵ of ≥15 mmHg
Oral body temperature [°C]	High	≥ 38.4°C	≥ 39.1°C
	Low	≤ 35.0°C	
Pulse rate [bpm] ²	High	2-3 years	> 128
		3-4 years	> 123

Vital sign	Patient age at visit				
		< 18 years	≥ 18 years		

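### The laboratory part of secondary objective 9 is summarised only by the worst on-study value, so it gives no time course and tends to hide gradual or frequently sampled improvement

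*SAP*

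**What the plan says.** SAP 1.2 gives objective 9 as: "To assess changes in clinical assessments such as laboratory evaluation, vital signs and physical findings over time". SAP 3.6 then says that cardiac tests (ECG and BNP are its examples) and "laboratory assessments (e.g., D-dimer, fibrinogen, hemoglobin) as well as vital signs" will be assessed "between the index date and key time-points following the index date, appropriately by age groups".

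Protocol 6.8.2, under objective #9, sets the comparison as index against the key time-points of Table 6-1 and plans two displays. The first is a count: "The change in clinical assessments will be summarized as the number (%) of patients experiencing a change in each clinical assessment". The second is shift tables from the index date. It does not say which post-index value the shift tables use.

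For laboratory data the SAP specifies three summaries:

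- Worst post-baseline CTC grade: "Each patient will be counted only for the worst grade observed during study period".
- For graded tests: "Shift tables using CTC grades to compare index date to the worst collected value during study period".
- For tests without CTC grades: "shift tables using the low/normal/high/(low and high) classification to compare index date to the worst collected value during study period".

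Under SAP 1.3 the study period starts at the index date, so values from the first weeks on treatment are eligible to be the worst. In the same part of SAP 3.6, the height and BMI shift tables use the last available value, and height and weight SD scores are summarised by time window.

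**The concern.** A worst-value table is a toxicity display. It answers whether a patient was ever as bad as a given grade, which is the right question for safety. It does not answer whether the marker changed between index and a given time-point. A patient with a raised D-dimer at index and one raised value at week 4 appears as high-to-high even if every later value is normal. The more samples a patient has, the more chances there are for a bad one. Sample counts will differ: a patient starting on 23-Sep-2019 has 24 weeks to the cut-off, whereas those in the case series published in 2018 began at least 14 months before it.

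SAP 3.6 says the secondary endpoints are there to support efficacy and describe the effect on varied disease manifestations, as well as to evaluate safety. For laboratory data, the specified tables serve the safety purpose well and the others poorly.

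**Working it through.** **Step 1. Aim against outputs.** The documents give no figure for objective 9, so there is nothing to reproduce. Side by side:

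| Source | Post-index value compared with index | By time-point? |
|---|---|---|
| Protocol 6.8.2, number (%) with a change | Key time-points | Yes |
| Protocol 6.8.2, shift tables | Not specified | Not specified |
| SAP 3.6, opening sentence for #9 | Key time-points | Yes |
| SAP 3.6, worst CTC grade | Worst (no comparison) | No |
| SAP 3.6, CTC shift | Worst | No |
| SAP 3.6, low/normal/high shift | Worst | No |
| SAP 3.6, height and BMI shift | Last available | No |
| SAP 3.6, height/weight SD scores | Each time window | Yes |

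No listed laboratory output uses a time-point, the last value, or a change from index.

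**Step 2. Frequent sampling (assumed inputs).** Take a marker that was high at index and has improved, so that each of k later samples is normal with probability p, independently. The worst-value table shows it as abnormal with probability 1 − p^k.

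| p | k = 3 | k = 5 | k = 8 |
|---|---|---|---|
| 0.8 | 1 − 0.512 = 49% | 1 − 0.328 = 67% | 1 − 0.168 = 83% |
| 0.9 | 1 − 0.729 = 27% | 1 − 0.590 = 41% | 1 − 0.430 = 57% |

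A table using one value, such as the last, shows it as abnormal in 1 − p = 20% or 10%, whatever k is. Positive within-patient correlation pulls the worst-value figures down. With perfect correlation they fall to the same 20% or 10%, so at p = 0.8 and k = 5 the range is 20% to 67%.

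**Step 3. Gradual improvement (assumed inputs).** Suppose the mean starts 1 unit on the abnormal side of the limit, moves linearly to 1 unit on the normal side by week 24, and stays there. Simulating 200,000 patients per setting, keeping those abnormal at index, with within-patient SD 0.25 / 0.5 / 0.75, the percentage shown as normal is:

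| Samples at weeks | Worst value | Last value |
|---|---|---|
| 4, 12, 24 | 0.2 / 4 / 9 | 100 / 98 / 91 |
| 4, 12, 24, 36, 52 | 0.2 / 4 / 7 | 100 / 98 / 91 |

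Hand check for three samples and SD 0.5: the means are 0.67 at week 4, 0 at week 12 and −1 at week 24. The chance that all three are normal is 0.091 × 0.5 × 0.977 = 0.044, which agrees with the 4%.

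**Step 4. The favourable case.** If improvement is complete before the first post-index sample, the worst-value table shows it in 100 / 93 / 75% of patients with three samples and 100 / 89 / 62% with five. How much is hidden therefore depends on how fast the marker responds and how often it is measured.

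**The case against.** Several points on the other side have force.

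- **General rules.** SAP 3.6.1 gives the full set of descriptive statistics for continuous secondary data, and SAP 3.6.2 says that available data at each time-point will be used. With the opening sentence for #9, these could be read as permitting laboratory summaries by window. However, neither section calls for one, and a programmer working from the laboratory list would produce only the three worst-value outputs.
- **Graded tests.** A shift from grade 3 at index to a worst grade of 1 shows improvement without normalisation. This stands: Steps 2 and 3 cover only the normal/abnormal split.
- **Invented inputs.** The probabilities, sample counts and trajectories are not in the documents, and independence overstates the effect. This stands too; the figures are illustrations.
- **Role of the markers.** D-dimer, fibrinogen and hemoglobin appear only as example laboratory tests, and BNP is listed under cardiac assessments. Neither document calls them efficacy biomarkers. The point rests on the stated aim of change over time, not on such a status.
- **Undeclared departure.** A reader might infer that SAP Section 2 conceals a change to the shift tables. The documents do not support that: the protocol left the post-index value open. What is not delivered is the protocol's count of patients with a change at key time-points.
- **Redaction.** Text after SAP 3.6.2 is blacked out and may hold other analyses. It is not counted as missing.

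**Conclusion.** The point holds for the laboratory component of objective 9. The aim is change from index to key time-points; every laboratory summary specified uses the worst value. The plan as written gives no laboratory time course and does not deliver the protocol's count. It tends to hide improvement that is gradual or frequently sampled. Under the assumptions of Step 2, an improved marker with p = 0.8 still appears abnormal in 49%, 67% and 83% of patients with 3, 5 and 8 samples, and in fewer if samples are positively correlated.

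Two stronger readings are tempting but unsupported. One is that objective 9 goes unanswered as a whole: growth measures are summarised by window or last value, and vital signs are listed in full with notable values counted, so neither is affected. The other is that these tables can hardly ever show benefit: improvement appears whenever every on-study value falls in a better category or grade than at index, and Step 4 shows this can be common if response is fast.

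The study is descriptive and its primary endpoint is untouched. The amendment is still worth making, because it is cheap and supplies what both documents set out to report.

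**What to change.** Keep the three worst-value summaries and label them as safety displays. For the laboratory and cardiac markers named under objective 9 (D-dimer, fibrinogen, hemoglobin and BNP), add to SAP 3.6:

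- observed value and change from baseline in each Table 3-1 window (N, mean, SD, median, Q1, Q3, minimum, maximum), using the baseline definition in SAP 4.1 and the rule in SAP 3.3 for choosing among several values in a window;
- a shift table from index to the Week 24 value, and another to the last on-treatment value, each with the number (%) of patients improved, stable or worsened. The favourable direction should be fixed in advance for each marker.

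The cost is one SAP paragraph and a few tables from data already abstracted. N will be small in some windows; the existing rule in SAP 3.3, which displays only time-points with data for at least 10% of patients, handles that.
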